## 4. STUDY DESIGN

### 4.1. Overall Design

This is a single-center, 2-part Phase I/IIa study to evaluate the safety, tolerability, clinical effect and systemic exposure potential of topically applied GSK2981278 ointment in subjects with plaque psoriasis. Drug delivery into the skin and changes in the relevant biomarkers will be explored using skin punch biopsies as well.

- Part A: open label, single arm study
- Part B: double-blind, randomized, 2-arm, parallel-group, vehicle-controlled study

After completion of Week 4 assessments and Week 8 assessments in Part A, the Sponsor will review the safety, tolerability, PK and clinical effect data. If data demonstrates a mean percent reduction of 40% or greater in TPSS from baseline and systemic exposure levels below the NOAEL determined in the pre-clinical toxicity studies without significant safety or tolerability issues at either time point, the study will proceed to Part B.

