## Overall Design

This is a single-center, 2-part Phase I/IIa study to evaluate the safety, tolerability, clinical effect and systemic exposure potential of topically applied GSK2981278 ointment in subjects with plaque psoriasis. Drug delivery into the skin and changes in the relevant biomarkers will be explored using skin punch biopsies as well.

- Part A:** open label, single arm study
- Part B:** double-blind, randomized, 2-arm, parallel-group, vehicle-controlled study

After completion of Week 4 assessments and Week 8 assessments in Part A, the Sponsor will review the safety, tolerability, PK and clinical effect data. If data demonstrates a mean percent reduction of 40% or greater in TPSS and systemic exposure levels below the no observed adverse effect level (NOAEL) determined in the pre-clinical toxicity studies without significant safety or tolerability issues at either time point, the study will proceed to Part B.

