#### **4.4. Design Justification**

Single-arm, open-label Part A will allow focused evaluation of safety, tolerability, clinical effect, and systemic exposure potential and the exploration of drug delivery to the skin and changes in relevant gene expressions following topically applied GSK2981278 ointment in a small number of subjects without exposing additional subjects to unnecessary burdensome assessments.

Treatment duration of 8 weeks is considered sufficiently long to look for the signal of drug effect and determine whether GSK2981278 may be a viable candidate for development as a topical treatment for plaque psoriasis.

The number of subjects proposed in this study is expected to provide reasonable information on the clinical effect, gene expression changes, and drug delivery into the psoriatic skin.

[figure not shown]
If data from Part A demonstrate sufficient signal of drug effect to meet the pre-defined criteria to proceed to Part B, any clinical effect observed in Part A will be further evaluated in a randomized, double-blind, vehicle-controlled fashion in Part B. Inclusion of the vehicle group will inform the treatment effect relative to the vehicle effect.

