### 9.2. Sample Size Considerations

#### 9.2.1. Sample Size Assumptions

Sample size is based on feasibility and the estimated number of subjects expected to provide reasonable information on the key objectives of the study.

For Part A:

Summary statistics, such as mean % of reduction in TPSS, mean % reduction in PGA and mean % of reduction in PASI will be estimated. With 8 evaluable subjects, precisions on these estimates are assessed as below.

Endpoint	Assumptions	Sample Size	95%CI estimate
Mean % reduction in TPSS	50% reduction with 20% standard deviation will be observed	N=8	33.3% - 66.7%
Mean % reduction in PGA	50% reduction with 30% standard deviation will be observed	N=8	24.9%-75.1%
Mean % reduction in PASI	50% reduction with 25% standard deviation will be observed	N=8	29.1% -70.9%

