### **9.3.2. Interim Analysis**

No interim analysis is planned.

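### Does the wording of the Part A go rule leave open whether the study should proceed to Part B?

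*Protocol*

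**What the plan says.** The Protocol synopsis (Overall Design) and section 4.1 carry the same rule. Two sponsor reviews are named: "After completion of Week 4 assessments and Week 8 assessments in Part A". The next sentence sets the condition. It opens with "If data demonstrates a mean percent reduction of 40% or greater in TPSS from baseline and systemic exposure levels below the NOAEL" and ends with "without significant safety or tolerability issues at either time point, the study will proceed to Part B". The synopsis version differs only in lacking the reference to baseline: "If data demonstrates a mean percent reduction of 40% or greater in TPSS and systemic exposure levels below".

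Section 4.4 treats the rule as fixed in advance, speaking of "sufficient signal of drug effect to meet the pre-defined criteria to proceed to Part B", but does not restate it. Section 3 places the Part A TPSS endpoint at Week 8 without linking it to the go rule. Section 9.2.1 assumes for Part A TPSS that "50% reduction with 20% standard deviation will be observed", with 8 evaluable subjects. Section 9.3.2 says "No interim analysis is planned".

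**The concern.** The final phrase of the go sentence can attach in two ways.

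1. It governs the whole condition. Meeting every criterion at Week 4, or every criterion at Week 8, opens Part B.
2. It governs only the safety clause. A significant issue at Week 4 or at Week 8 blocks Part B, and no visit is given for the TPSS and exposure criteria.

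The word for one or the other visit therefore loosens the rule on the first reading and tightens it on the second. Suppose the mean TPSS reduction is 45% at Week 4 and 35% at Week 8, with all else acceptable. That is a go if one visit suffices and a no-go if Week 8 governs. The decision commits about 18 further subjects. Part A is open label, so in principle the reading could be settled after the data are known, although section 4.4 calls the criteria pre-defined.

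**Working it through.** **Which reading the text supports.** The only antecedent for the two time points is the preceding sentence, which names the Week 4 and Week 8 reviews and says that safety, tolerability, PK and clinical effect are all looked at. The Part A Time and Events Table (7.1) fits this. Day 29 and Day 57 each have the same seven-sample, 10-hour plasma profile, while Day 15 has two samples. TPSS, ECG, laboratory tests and application site tolerability are also done at both Day 29 and Day 57. Every criterion can be judged at each review. If only Week 8 counted, the Week 4 review of PK and clinical effect would serve no go decision. This favours reading 1.

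**Inputs.** N=8, SD 20% and true Week 8 mean 50% (9.2.1); cut-off 40% (4.1). The Week 4 mean and the correlation between visits are not in the Protocol and are assumed below.

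**Plan's own figure.** SE = 20/√8 = 7.07. The 95% interval is 50 ± 2.365 × 7.07 = 50 ± 16.7, or 33.3% to 66.7%, as stated in 9.2.1.

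**Chance of meeting the TPSS cut-off.** For true mean m at one visit, p = Φ((m − 40)/7.07). For either visit, p4 + p8 − P(both), with P(both) from a bivariate normal at correlation 0.5 and 0.8.

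| True mean, Week 4 / Week 8 | Week 8 governs | Either visit suffices |
|---|---|---|
| 25% / 50% | Φ(1.414) = 0.921 | 0.921 |
| 30% / 50% | 0.921 | 0.922 to 0.921 |
| 45% / 50% | 0.921 | 0.953 to 0.931 |
| 40% / 40% | Φ(0) = 0.500 | 0.667 to 0.602 |

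Third row: p4 = Φ(0.707) = 0.760 and P(both) = 0.729 to 0.751, so either = 0.760 + 0.921 − P(both). Last row: P(both) = 1/4 + arcsin(ρ)/(2π) = 0.333 to 0.398, so either = 1 − P(both).

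The gap is 0 to 3 points at the plan's effect and 10 to 17 points when the true mean sits exactly on the cut-off. If the Week 4 mean is also 50%, the either-visit figure is 0.947 to 0.985 (correlation 0.9 to 0.3), a gap of 3 to 6 points.

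**A wrong go.** Take the 20% reduction that 9.2.1 assumes for vehicle in Part B, at both visits. Week 8 alone passes with chance Φ(−2.83) = 0.002. Either visit passes with chance at most 0.005. Both readings stop an ointment that does no better than that.

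**Safety clause.** A Week 8 issue after a clean Week 4 separates the readings only if TPSS and exposure also passed at Week 4. For assumed Week 4 means of 25%, 30% and 45%, the TPSS part of that has chance 0.017, 0.079 and 0.760. If TPSS has not reached 40% by Week 4, the result is no-go on both readings.

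**The case for a change.** The strongest case is that a rule described as pre-defined should be capable of only one answer, and that the gap can be made large. If both visits must pass and the Week 4 mean is 30%, the chance of a go falls from 92% to about 8%. If the effect fades from 50% at Week 4 to 30% at Week 8, it is 92% with either visit and 8% with Week 8. Amendment 1 edited this very sentence in 4.1 and left the visit open.

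The grammatical point stands: nothing elsewhere in the Protocol rules out the second attachment. A tolerability issue at Week 4 that has resolved by Week 8, with every criterion then met, is a go on reading 1 and a no-go on reading 2, whatever the Week 4 TPSS result.

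The large numbers carry less weight. No passage requires the cut-off at both visits, and the 8% also needs an assumed Week 4 mean. Nothing in the Protocol suggests an effect that fades under continued treatment. Nor would naming visits make the gate mechanical, because what counts as a significant safety or tolerability issue remains a judgement. A later safety problem is not left without provision: 5.4.3 and 6.4 apply under either reading, and 10.5 lets the sponsor suspend or stop the study at any time. A TPSS effect not sustained after a Week 4 go is what the vehicle-controlled Part B would then examine.

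The statement in 9.3.2 is not in conflict. A review between an open-label part and a separate randomised part is not an interim look at the Part B comparison.

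**Conclusion.** The ambiguity is real but minor, and no change follows. The text and the visit schedule point to one sensible reading, that all criteria may be met at the Week 4 or the Week 8 review, and the sponsor can apply it without further text. Against the main alternative, with Week 8 governing, the chance of passing the TPSS criterion moves by about 0 to 3 points at the plan's 50% effect (Week 4 mean assumed 25-45%) and by 10 to 17 points at a true 40% at both visits, with correlation assumed 0.5 to 0.8 throughout. Only an effect assumed to fade gives a large gap.

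No stated figure or rule is shown to be wrong, and the choice of reading belongs to the sponsor. Part A subjects cannot enter Part B (4.3), so the route by which Part B is opened does not affect its randomised comparison, for which section 9.1 plans no formal hypothesis test. Naming a visit for each criterion would tidy the sentence but would leave Part B's conclusions as they are.

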### 4.2. Treatment Arms and Duration

This study will consist of 3 periods: the screening period of up to 4 weeks, the treatment period of 8 weeks, and the follow-up period of 2 weeks. Study visits will occur at

Screening; Baseline; Weeks 1, 4, and 8 during the treatment period; and Week 10 for follow-up, which will be 2 weeks after the last application of study treatment. Additional visits may occur, as needed, for early withdrawal or to follow-up on any skin reactions or ongoing AEs. A subject's total duration of study participation will be approximately 14 weeks.

In **Part A**, subjects will receive topical application of GSK2981278 4% ointment to all affected areas of the body twice daily for 8 weeks.

In **Part B**, subjects will receive topical application of either GKS2981278 4% ointment or the vehicle ointment, according to the randomization, to all affected areas of the body twice daily for 8 weeks.

The concentration of GSK2981278 may be lowered to 2% or 0.8% in Part A and/or Part B based on the newly available safety and tolerability data. Refer to Section [6.4](#) for planned dose adjustments.

#### **4.3. Type and Number of Subjects**

In **Part A**, eight adult subjects with chronic stable plaque psoriasis will be enrolled. If subjects prematurely discontinue the study treatment, additional replacement subjects may be recruited at the discretion of the Sponsor in consultation with the investigator.

In **Part B**, approximately 18 adult subjects with chronic stable plaque psoriasis will be randomized with an allocation ratio of 2:1 to GSK2981278 4% ointment or vehicle ointment to have at least 15 evaluable subjects who comply closely with the protocol (e.g. have sufficient exposure and critical assessments completed). Subjects who were enrolled in Part A will not be eligible to participate in Part B.

If the concentration of GSK2981278 is lowered in either part of the study, additional subjects may be enrolled to have the minimum evaluable subjects in that part treated with the lower concentration of study treatment.

#### **4.4. Design Justification**

Single-arm, open-label Part A will allow focused evaluation of safety, tolerability, clinical effect, and systemic exposure potential and the exploration of drug delivery to the skin and changes in relevant gene expressions following topically applied GSK2981278 ointment in a small number of subjects without exposing additional subjects to unnecessary burdensome assessments.

Treatment duration of 8 weeks is considered sufficiently long to look for the signal of drug effect and determine whether GSK2981278 may be a viable candidate for development as a topical treatment for plaque psoriasis.

The number of subjects proposed in this study is expected to provide reasonable information on the clinical effect, gene expression changes, and drug delivery into the psoriatic skin.

[figure not shown]
If data from Part A demonstrate sufficient signal of drug effect to meet the pre-defined criteria to proceed to Part B, any clinical effect observed in Part A will be further evaluated in a randomized, double-blind, vehicle-controlled fashion in Part B. Inclusion of the vehicle group will inform the treatment effect relative to the vehicle effect.

#### 4.5. Dose Justification

In this study, the clinical effect of GSK2981278 will be evaluated in patients with psoriasis at a 4% w/w dose applied topically to up to 15% of total body surface area for 8 weeks as an ointment. Data from ex vivo target engagement studies, the first study in humans, and repeat dose toxicity studies in rat (oral) and minipig (oral and dermal) were considered for the selection of the concentration of GSK2981278 ointment in this study.

In ex vivo human skin following single dermal application of GSK2981278 with the current clinical formulation at concentrations ranging from 0.01 to 4%, a potent dose-dependent inhibition of Th17 signature cytokines mRNA levels was observed with effect reaching plateau after 0.1% concentration (Figure 1). Based on this data, concentrations ranging from 0.03% to 4% are being considered in the early phase clinical trials. In this study, using a single concentration of GSK2981278 ointment, the highest concentration 4% is selected to maximize the probability of observing the clinical effect of GSK2981278 in patients with psoriasis.

**Figure 1 Percent maximum expression of IL-17A transcripts in ex-vivo human skin**

In the first clinical study (201465), once daily treatment of GSK2981278 at 0.03%, 0.1%, 0.8% and 4% w/w each applied to a small area of a psoriatic plaque ( $1.13 \text{ cm}^2$ ) over 19 days was well tolerated in patients with psoriasis although reduction in the inflammatory infiltrate thickness measured by ultrasound was not observed for any of the tested concentrations.

GSK2981278 has been evaluated in repeat dose toxicity studies following oral administration for up to 13 weeks in rats and minipigs; following dermal administration for up to 13 weeks in minipigs.

No dose-limiting toxicities were observed in any of the nonclinical toxicity studies, hence the NOAELs for systemic effect were established at the highest tested dose levels.

The NOAEL established for systemic effects in the oral 13 week rat study was 200 mg/kg/day. The end of study area under the concentration-time curve (AUC) and maximum plasma concentration ( $C_{max}$ ) values at 200 mg/kg/day in rats were 302 ng.h/mL (males) and 4650 ng.h/mL (females) and 79.5 ng/mL (males) and 3390 ng/mL (females), respectively.

The NOAEL established for systemic toxicity in the dermal 13 week minipig study using the current clinical formulation was 140 mg/kg/day (7%; twice daily (BID); 10% body surface area). The end of study AUC and  $C_{max}$  values at 140 mg/kg/day were 325 ng.h/mL and 52.4 ng/mL (gender average mean), respectively.

The predicted human AUC at steady state is 58.5 ng.h/mL and  $C_{max}$  is 2.4 ng/mL (4% GSK2981278 [maximum concentration] applied twice daily to 15% body surface area [BSA]). Multiples of predicted mean human exposure for AUC and  $C_{max}$  at the NOAEL for systemic findings in the rat (oral) and in the minipig (dermal) are shown in [Table 1](#).

**Table 1 Predicted mean human exposures with 90% prediction intervals (PIs) for GSK2981278 ointment at 4% (w/w) and calculated mean safety covers with 90% PIs.**

BSA Treated (%[cm  ] a )	Mean Predicted Human Exposure b at steady state (PI)		Mean Safety Cover-Fold Difference (PI)					
			13 Week Rat (Oral – Males)		13 Week Rat (Oral – Females)		13 Week Minipig (Dermal – Gender Averaged)	
	$C_{max}$ (ng/mL)	AUC 0-24h (ng.h/mL)	$C_{max}$	AUC 0-24h	$C_{max}$	AUC 0-24h	$C_{max}$	AUC 0-24h
15 [2595]	2.4 (2.0 – 2.9)	58.5 (47-70.5)	33 (27 – 41)	5 (4 – 6)	1413 (1153 – 1730)	79(66 – 99)	21 (17 – 26)	6 (4 – 7)
5 [865]	0.8 (0.7 – 1.0)	19.5 (15.7 – 23.5)	98 (81 – 122)	15 (13 – 19)	4170 (3460 – 5189)	238(198 – 297)	64 (51 – 77)	17 (13 - 20)

**Key:**

a=equivalent area of skin in cm^2 for a standard BSA of 1.73 m^2

b=calculated using BSA in cm^2 for BSA of 1.73m^2

The planned twice daily application of GSK2981278 ointment at 4% w/w concentration to up to 15% of total BSA in this study provides a safety cover of  $\geq 5$  fold for AUC and  $\geq 21$  fold for  $C_{max}$  for systemic effect.

In a 13-week dermal minipig study, test article-related adverse dermal irritation was observed. Dermal irritation included slight to marked erythema and eschar in most animals at all dose levels and ulceration, tissue damage, exfoliation and desquamation in less than 5 animals. A NOAEL was not established for this effect. However, there was no clear dose-response in the incidence and/or severity of clinical and microscopic skin findings, and irritation was reversible with treatment discontinuation. These findings were not observed with the same formulation in a 4 week dermal study in minipigs. No skin irritation findings have been observed in mice, rats or rabbits. In addition, the formulation with GSK2981278 was not a contact sensitizer in the mouse local lymph node assay, was not classified as an eye irritant in the bovine corneal opacity and permeability assay at concentrations up to 7%, and has no potential for phototoxicity in nonclinical models

The dermal minipig high dose concentration at 4% of GSK2981278 was equivalent to 960  $\mu\text{g}/\text{cm}^2$ . When the minipig dose levels are compared with the clinical dose levels at a concentration 4% of GSK2981278, equivalent to 63  $\mu\text{g}/\text{cm}^2$ , there is a 15 fold difference, indicating patients participating in this study will receive a 15 fold lower dose on a  $\mu\text{g}/\text{cm}^2$  basis than minipigs received in the 13 week study due to the difference in the volume applied. In addition, even when compared with the lowest dose concentration tested in minipigs, 1%, the clinical dose at 4% concentration is almost 4 fold lower on a  $\mu\text{g}/\text{cm}^2$  basis.

Patient's skin will be monitored for any signs of irritation using the application site tolerability scale at Days 1, 15, 29, and 57 in addition to regular AE/SAE monitoring, and with phone contact with patients at Days 8 and 43. In the event of skin irritation, study treatment will be discontinued according to the stopping criteria (Section 5.4.3).

Findings from preclinical in vivo pharmacology and toxicology studies with GSK2981278 have provided reasonable assurance that there are no undue or unforeseen risks for the administration of GSK2981278 to humans at up to 4% concentration twice a day to up to 15% BSA in this study (GlaxoSmithKline Document Number [2016N286376\\_00](#) GSK2981278 Investigator's Brochure).

#### **4.6. Benefit:Risk Assessment**

Summaries of findings from both clinical and non-clinical studies conducted with GSK2981278 can be found in the Investigator's Brochure (IB). The following section outlines the risk assessment and mitigation strategy for this protocol:

#### 4.6.1. Risk Assessment

Potential Risk of Clinical Significance	Summary of Data/Rationale for Risk	Mitigation Strategy
Investigational Product (IP) [GSK2981278]		
Skin irritation or allergic reaction to GSK2981278 or to components of its vehicle.	
GSK2981278 was not a contact sensitizer in the mouse local lymph node assay and was not classified as an eye irritant in the bovine corneal opacity and permeability assay at concentrations up to 7%.
 
GSK2981278 is a sulphonamide, chemically distinct from the antibiotic sulphonamides that are one of the most common causes of drug reactions. GSK2981278 does not contain the arylamine group that is known to be associated with allergies and hypersensitivity as the antibiotic sulphonamides do. Evidence suggests no cross-reactivity between arylamine sulphonamides and non-arylamine sulphonamides [Brackett, 2007; Strom, 2003].
 
In a 13-week dermal minipig study test article-related adverse dermal irritation was observed in a non-dose responsive manner and included marked erythema and eschar with occasionally ulceration, tissue damage, exfoliation and desquamation. A NOAEL was not established for this effect, although a systemic NOAEL was achieved at 7% concentration BID. There was no clear dose-response in the incidence and/or severity of clinical and microscopic skin findings, and irritation was reversible with treatment discontinuation. These findings were not observed with the same formulation
	
Potential subjects with a known or suspected intolerance to the components of GSK2981278 vehicle will be excluded.
 
Subjects will be informed of the sulphonamide nature of the compound via informed consent. Subjects will not be excluded from the trial solely based on a history of sulphonamide allergy.
 
The skin will be evaluated for any signs of allergic reaction or excessive irritation in addition to a regular AE/SAE monitoring.
 
If a subject experiences application site reaction, the study treatment may be discontinued temporarily or permanently (see Section 5.4.3).

Potential Risk of Clinical Significance	Summary of Data/Rationale for Risk	Mitigation Strategy
	
in a 4 week dermal study in minipigs. No skin irritation findings have been observed in mice, rats or rabbits.
 
In the one and only clinical study conducted to date with GSK2981278, study 201465, the physical examination of the skin did not show any findings in any of the 15 subjects treated with GSK2981278 in small areas (1.13 cm^2) of the plaque over 19 days.
	
Systemic reactions including but not limited to end organ toxicity.	
No adverse GSK2981278-related systemic findings have been observed up to 13 weeks duration in an oral rat study, 13 week oral minipig study, or 13 week dermal minipig study at doses up to 200 mg/kg/day, 30 mg/kg/day, or 140 mg/kg/day, respectively.
 
GSK2981278 did not produce acute cardiovascular effects in minipigs or respiratory or neurobehavioural effects in rats in safety pharmacology studies at doses up to 30 and 200 mg/kg, respectively. GSK2981278 inhibited hERG tail current recorded from HEK 293 cells stably transfected with hERG cDNA, with an IC25 of 2.2 µM (1.02 µg/mL) or 100000 times greater than the predicted human free Cmax.
 
One AE of nasopharyngitis, considered unrelated to study treatment, was reported and no SAEs were reported in study 201465. No remarkable changes in laboratory tests, ECGs or vital signs were reported in this study.
	
Standard laboratory tests, ECGs and physical examinations will be performed and vital signs will be reviewed
 
Subjects will be monitored for the occurrence of AEs/SAEs throughout the study.

Reproductive and developmental toxicity	GSK2981278 administered to pregnant rats orally up to	Only females of non-reproductive potential will

Potential Risk of Clinical Significance	Summary of Data/Rationale for Risk	Mitigation Strategy
	
200 mg/kg/day or dermal administration in a preliminary dose-range finding rabbit study up to 7% concentration resulted in no maternal or developmental toxicity.
 
No effects on testes were reported in repeat dose toxicity studies.
	
be enrolled in this study.
 
In addition, male subjects with female partners of child bearing potential will be required to use a male condom unless vasectomy was done and azoospermia was documented.

Study Procedures		
Worsening of psoriasis symptoms	
Subjects discontinuing their current psoriasis treatment may experience a worsening of their psoriasis during the washout period before beginning treatment in this study. A worsening of psoriasis may also occur during the active treatment period.
 
Patients did not discontinue the study 201465 due to worsening of psoriasis symptoms.
	
The informed consent for this study will state the risk of worsening of the symptoms of psoriasis.
 
Subjects who either choose to withdraw or are withdrawn from the study treatment because they meet withdrawal/stopping criteria will be able to use alternate treatments for their psoriasis.

Punch biopsy	
Local bleeding and bruising, pain, infection, allergic reaction (e.g. to a disinfectant or an anaesthetic agent) or damage to the structures beneath the skin (such as an artery or nerve) may occur. Scarring may occur at the biopsy site.
	
Staff performing the procedures will be adequately trained and subjects will be informed about potential risks. Local anaesthesia will be used prior to obtaining biopsies. Proper wound care (e.g. application of pressure, bandage, etc.) will be provided as needed and subjects will be checked for wound healing at the follow-up visit. Pain medication (e.g. ibuprofen) will be allowed.

